| Carbon Monoxide Level | CO Analyzer PICO+ ¹¹⁵ | ✓ | | ✓ | ✓ | ✓ |
| Satisfaction Survey | | | ✓ | | | |

Table 2. COVID-Related Component Assessment Schedule

| Aim 1: | Instrument | Baseline | | 6 wk | 12 wk |
|---|---|----------|---|------|-------|
| Knowledge and use of measures to prevent catching and spreading virus | Measure to be developed as part of project | ✓ | | ✓ | ✓ |
| Aim 2: | | | | | |
| Use of healthcare for COVID-related issues | Self-reported service use and record review | ✓ | | ✓ | ✓ |
| Social determinants of health | UCLA Loneliness Scale ¹²⁴ | ✓ | | ✓ | ✓ |
| | Lubben Social Network Scale-6 ¹²⁵ | ✓ | | ✓ | ✓ |
| | Social Connectedness (items developed for this project) | ✓ | ✓ | ✓ | ✓ |

5. Study Progress Monitoring

Upon completion of trainings, promotion and recruitment will begin at both Seven Counties Kentucky and Centerstone Tennessee. [name] and [name], the site PIs in Kentucky, will facilitate the research team's access to the clinical treatment teams at Seven Counties Kentucky to identify potentially eligible participants and [name] will facilitate access at Centerstone Tennessee. In addition, the Site PIs will ensure that the research staff have access to information needed in the electronic medical record to efficiently screen potential participants. Both Site PIs will participate in the weekly project meetings with Dartmouth to discuss pre-implementation and implementation tasks as well as dissemination of outcomes for the project. [name], [name], and [name] will provide the administrative supervision to the site research staff and will periodically attend meetings of the Key Stakeholder Advisory Group and Consumer Advisory Group.

In addition to enrolling participants, the research staff hired for this project will be responsible for all data collection required for this project. The Research Coordinators and Research Interviewers will conduct baseline assessments with participants; while only the blinded Research Interviewer will conduct research assessments at 4, 8, and 12 months follow-up. The Research Coordinators will conduct the 8-week phone call to assess satisfaction with the study interventions. The Research Coordinators will manage an account to provide reimbursement to participants for completing research interviews. They will also assist in coordination of the Consumer Advisory Group meetings and the Key Stakeholder Advisory Group quarterly meetings.

A schedule of weekly calls will be scheduled with the Dartmouth team for supervision of the research staff and for fidelity assurance of the I-IMR and CDSMP models. The Research Coordinators and the Research Interviewers will participate in these weekly meetings and the intervention facilitators will participate in weekly fidelity assurance calls. Intervention facilitators will audio or video record (mode will depend on whether the sessions are being delivered remotely or in-person) CDSMP and I-IMR sessions and submit recordings to the Dartmouth team for review and feedback each week.

[name], Director of Peer Support Services at Centerstone Kentucky, will be an integral member of the project team. She will participate in the weekly project management meetings with the Dartmouth team and will also facilitate monthly phone meetings of the Consumer Advisory group with [name]. [name] and the other 2 Peer Advisors from Kentucky will travel annually to Tennessee with [name] for an in-person meeting with the 2 Peer Advisors from Centerstone Tennessee.

6. Risks & Benefits

Note: Risks may be physical, psychological, social, legal, economic, to reputation, or others.

a. Describe any potential risks, their likelihood and seriousness:

The risks associated with participation in the study are deemed to be minimal and are outweighed by the potential benefits. Participation in an illness self-management group, like CDSMP or I-IMR, is no greater than participating in similar skills training groups as part of usual mental health care. Anxiety, boredom, or related discomfort could occur during self-management sessions or during research interviews. There is also a risk of loss of confidentiality from participating in a group, participating in research assessments, and using the mobile app (associated with I-IMR).

b. Confirm that risks to subjects have been minimized, by use of procedures which are consistent with sound research design and which do not unnecessarily expose subjects to risk:

Anxiety or discomfort during illness self-management groups and during interviews will be handled by trained facilitators/interviewers who will work individually with participants to develop and enact strategies to cope and reduce distress during the groups. Breaks will be offered during both groups and interviews as needed as well. Risks regarding breach of confidentiality with respect to the study data will be minimized in several ways. First, we will use using code numbers instead of names on the data.

The data collected using codes will be electronically captured on REDCap, a secure data collection program. The code will be unavailable to anyone outside of the research team, and it will be destroyed at the conclusion of the project. With respect to the data that is collected by the smartphone application, data are transmitted to ZCO (software development company for the smartphone application) server via secure, HIPAA-compliant security protocol over secure cellular connection. The data transmitted during sessions do not include participant identifiers.

c. Describe why all the risks to subjects are reasonable in relation to both anticipated benefits and the knowledge expected to be gained from the study:

The risk to participants is minimal and outweighed by the potential benefit of improving self-management of illness prompting to engage in illness management and positive coping behaviors,

7. Unexpected Events or Incidental Findings

Describe potential events and provide a plan of action:

Serious, unexpected adverse events (SAE) related to study participation are rare in our research groups' studies. If an SAE occurs, the Co-PIs will report the event to the Dartmouth CPHS and to the DSMB. The Co-PIs, in consultation with Co-Is and others as needed, will review the adverse event report and gather other information as needed to investigate the event and determine the need for subsequent action. Any subsequent action will be documented and reported to the Dartmouth CPHS.

8. Deception

Does any part of this study involve deception or withholding of information from participants?

Yes No

If Yes, provide an explanation which addresses the following:

- A description of the deception being used
- Why the deception is necessary
- A plan for debriefing, or providing subjects with the pertinent information after participation

9. Equitable Participant Selection

a. Estimated number of participants at Dartmouth CPHS reviewed sites:

600 Adults 18+ and 150 of consented participants will also participate in the COVID-19 enhancement.

b. Provide a justification of the proposed sample size

The sample size is based on maintaining an adequate sample for data analyses with consideration to retention based on previous studies. Retention in our previous studies and in our IIMR studies has been very high. We conservatively estimate a loss of 20% over the 12-month study, resulting in full follow-up data on $n = 480$.

c. Define the target population:

The target population are individuals diagnosed with a SMI (diagnosis of schizophrenia, schizoaffective disorder, bipolar disorder, chronic depression with moderate impairment in functioning, PTSD, or other serious anxiety disorders) with co-morbid chronic medical problems receiving services at Seven Counties Services (KY) and Centerstone (TN) who reflect the racial, cultural, linguistic, and ethnic diversity of people with SMI in this agency.

Inclusion and Exclusion Criteria: Eligibility for the study also includes: diagnosis of a chronic medical condition increasing risk of early mortality from cardiovascular or respiratory disease or diabetes, hyperlipidemia, hypertension, COPD [including emphysema], asthma, coronary artery disease, heart failure, tobacco dependence, obesity), chronic pain, and at least 1 ER visit or hospitalization within the past year (and/or 3 or more unscheduled outpatient visits) or judgment by the treatment team of substantial need for illness self-management training. Consumers who do not speak English will be excluded for logistical reasons. Consumers with either no, or a well-controlled medical condition will not be included. Individuals residing in a nursing home or other institution will be excluded given the focus on independent management of illness. Because I-IMR and CDSMP involve learning new skills, individuals with a chart diagnosis of dementia, or evidence of significant cognitive impairment as indicated by the Saint Louis University Mental Status Examination⁷³ score <20 , will be excluded. Temporarily during the COVID-19 pandemic, participants who score <20 on the TICS will be excluded.

d. Vulnerable populations

Note: Certain populations are considered vulnerable to coercion and undue influence and are provided with additional protections when participating in a research study.

Identify any of the below populations which you plan to recruit for this study. In addition, complete the form(s) linked with each population as necessary and upload on the ‘Supporting Documents’ page in Rapport.

- [Pregnant Women, Fetuses and Neonates](#)
- [Children](#)
- [People with impaired decision-making capacity](#)

The following populations may also be considered vulnerable to coercion or other undue influence:

- Prisoners
- People who are economically disadvantaged
- The elderly
- People who are illiterate or do not speak English
- Students and employees

Describe any other potentially vulnerable population(s) and the additional protections provided to them:

10. Recruitment

Describe method(s) of recruitment. Associated advertisements and other materials to be used for recruitment should be uploaded to the ‘Consent Forms and Recruitment Materials’ page in Rapport.

We will use several approaches that have had proven effectiveness in prior studies with similar populations to ensure that all potentially eligible consumers are aware of the opportunity to participate in the project and that enrolled participants are retained. Potentially eligible consumers will be identified initially through a review by the site research staff of the electronic health record (EHR) and elicitation of referrals from the mental health treatment teams. Posters and pamphlets describing the project will also be distributed in the waiting rooms at the study sites. Letters will be sent to potentially eligible participants to ensure that all consumers who may qualify are aware of the study. Potential participants will be invited to group events to hear descriptions of the study. Email blasts and social media venues will be used to stimulate self- and clinical referrals to the study, and a description of the study will be included on the websites at the study sites. Following referral, the research staff will review eligibility criteria. Potentially eligible participants will be invited to meet with one of the research staff for an in-person verification of eligibility and an introductory description of the project and study requirements, including description of the study interventions, review of the study protocols, randomization, and required research assessments. Research introduction meetings have been successfully used by our research group to assure that study participants fully understand clinical and research procedures. In addition to enhancing the process of full informed consent, these procedures are designed to decrease the likelihood of study attrition due to inadequate appreciation of the time, effort, and component activities involved in participating in the intervention program, or in the study protocol.

11. Informed Consent, Assent, and Authorization

Interested individuals who have had an introduction meeting will then meet with a member of the research staff to review the informed consent form. Research staff will read the consent form word-for-word, stopping to check understanding after each paragraph. Competence to provide informed consent will be confirmed with a review of personal history and functioning and completion of an informed consent evaluation tool that will be designed for the study. If all goes well and the individual has a full understanding of the form, they will be asked to sign the consent agreeing to participate. Individuals with guardians will be able to participate as long as they are able to understand what the study involves. In these instances, assent will be obtained from the client and consent will be obtained from the legally designated guardian. Participants (and guardians) will be provided a signed copy of the consent form with contact telephone numbers if they have additional questions.

During the COVID-19 pandemic, we plan to consent new participants remotely. The staff providing services at Centerstone TN and Seven Counties have continued to make referrals of potentially eligible service users and the research staff have continued to chart screen potential participants for eligibility.

Following confirmation of eligibility, research staff will call potential participants to describe the details of the program and the research in the same way that it was presented to potential participants in person before the pandemic. Staff will mail a copy of the consent form to eligible and interested participants and schedule a time to review it, word-for-word, in a phone meeting, exactly as it would be reviewed in person, including administration of the consent evaluation. The research staff will obtain verbal consent, documenting this on REDCap, and requesting return of a signed copy of the consent form in a self-addressed, stamped envelope that will be provided to the participant.

a. Waiver(s) or alteration(s) may be requested for research that involves no more than minimal risk.

Indicate requested waiver(s) or alteration(s) below. In addition, complete the corresponding section of the [Waivers and Alterations Request Form](#) and upload it to the 'Consent Forms and Recruitment Materials' page in Rapport.

- For the informed consent *process*
- For the *documentation* of informed consent
- For the HIPAA Authorization to use and/or disclose PHI
- For a waiver of the requirement for medical record documentation

12. Compensation or Gifts

Please describe any payments, gifts or reimbursements participants will receive for taking part in the study:

All consented participants who are eligible will be paid \$50 each after completing the baseline and the 4 and 8 month study visits. Participants will receive \$25 for completing a satisfaction survey at 8 weeks and \$75 for completing an assessment at 12 months, for a total of \$250 per participant. Participants will not be taxed on any money received from this study since it is under the \$600 dollars per year minimum.

Individuals participating in the COVID-related needs assessment will receive \$50 for a one-hour qualitative interview. Research staff at Centerstone and Seven Counties will send a \$50 gift card by certified mail to the needs assessment participants. They will also send gift cards for completed research assessments for the COVID-related component (\$25 baseline, \$50 for 6 weeks, and \$75 for the 12 week) by certified mail.

13. Privacy of Participants

Note: Methods used to obtain information about participants may have an effect on privacy. For example:

- Consent discussions or interviews held in public which concern sensitive subjects or behaviors
- Observations of behavior, especially illicit behavior, in quasi-public settings

Describe any activities or interactions which could lead to a breach of privacy and provide a plan to protect participant privacy:

The research staff will be trained by Centerstone and Seven Counties Services in privacy standards such as the HIPAA privacy rule. Our research team is experienced in training, instrument

construction, editing, and data management at remote sites. We will use the same procedures for data acquisition and management used in prior studies, including: (1) a common core of initial and refresher training for staff collecting data; (2) continuous team feedback approach at the sites; and (3) final data editing and management at our facility in Concord, NH. Regular conference calls, including weekly assessment supervision, will also help ensure standardization of research procedures across sites, and identify quality control issues early, allowing consensus solutions to be reached. Weekly meetings of the research team provide an environment where quality assurance issues can be quickly identified.

14. Confidentiality of Data

Note: Any person engaged in research collecting information about illegal conduct may apply for a [Certificate of Confidentiality](#) from the National Institute of Health.

a. If disclosed, could any of the data collected be considered sensitive, with the potential to damage financial standing, employability, insurability, or reputation?

No Yes

If Yes, describe the data or information, the rationale for their collection, and whether a Certificate of Confidentiality will be obtained:

In order to participate in this study protocol, the participants must be receiving services at one of the community mental health centers. Although participation in mental health services and information related to receipt of services, such as mental health diagnosis, may be considered “sensitive,” we will not apply for a Certificate of Confidentiality as this would suggest that having a mental illness is akin to using illegal substances in that it could leave a person vulnerable to undesirable consequences related to employability, financial, legal status, etc. The suggestion that having a mental illness is something that requires protection from a Certificate of Confidentiality serves to further stigmatize individuals with mental illness, who should not be made to feel ashamed or compelled to hide the fact that they have a mental health diagnosis.

b. Describe the safeguards employed to secure, share, and maintain data during the study, addressing any of the following which may apply:

Risks regarding breach of confidentiality with respect to the study data will be minimized in several ways. First, we will use using code numbers instead of names on the data. The data collected using codes will be electronically captured on REDCap, a secure data collection program. The code will be unavailable to anyone outside of the research team, and it will be destroyed at the conclusion of the project. No medical records or protected health information shall be re-disclosed. A Certificate of Confidentiality will not be required. Other confidentiality protections include confidentiality training for all new staff and refresher seminars annually for all staff; removing or obscuring names from data forms; using an acronym in return addresses on correspondence to participants; and password-protected computer databases. The risks to participants will also be minimized by reporting on all findings in an aggregate, anonymous manner. In addition, data access will be restricted to members of

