This population and their social vulnerabilities also place them at disproportionate risk for COVID-19 acquisition, morbidity, and mortality.¹¹⁷⁻¹¹⁸ Many social vulnerabilities¹¹⁹ also increase risk of negative COVID-19 outcomes, including poverty, homelessness, and residence in congregate and transitional group homes, emergency shelters, and long-term care facilities where viral transmission has happened rapidly. Without specific training on COVID-19, these vulnerabilities will continue to be a source of unchecked community transmission that will have larger societal impacts.

We received funding to develop and evaluate the effectiveness of a 3-session I-IMR module to provide specific training on how to prevent contracting and spreading COVID-19 and other acute viral infectious diseases that may arise in the future and will similarly require: 1) knowledge and enactment of measures to maximize personal and societal safety (e.g., safely acquiring food, paying bills, accessing healthcare and COVID-related resources), 2) use of illness self-management behaviors to reduce risk of contracting and spreading illness, and 3) methods for addressing social determinants of health (e.g., maintaining social connection while ensuring physical distancing).

This component of the project will involve: 1) an initial needs assessment that will inform the refinement and specification of the training materials in the 3-session I-IMR COVID-19 and viral infectious disease module, 2) delivery of the module in phone or video-based sessions with a clinician trained in I-IMR, and 3) evaluation of the impact of the module on key outcomes. I-IMR participants will receive this 3-session module, which will be individually-delivered by phone or video (e.g., secure Zoom) to 75 participants (current and future participants assigned to I-IMR). We are not at liberty to add training on infectious viral diseases to CDSMP because this is not our intervention. The CDSMP participants are essential to the study as they serve as the comparison group, preserving the comparative effectiveness design, as required by PCORI.

2. Objectives and Hypotheses

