COVID-19 Enhancement Primary Aim: After co-design of the 3-session I-IMR module, we will evaluate the impact of the module by comparing participants assigned to I-IMR (n=75) to participants assigned to CDSMP (n=75) on the primary and secondary outcomes (**primary**: knowledge and use of measures to prevent contracting and spreading COVID-19; **secondary**: use of healthcare services for COVID-related concerns; perceived isolation and social disconnectedness).

Primary Hypothesis: I-IMR participants will demonstrate greater improvements in their scores on the primary outcome measure (a measure of knowledge and behaviors to prevent contracting and spreading COVID-19 developed for this project) compared to CDSMP participants.

Secondary Hypothesis: I-IMR compared to CDSMP participants will demonstrate less COVID-related health care service use and greater improvements in social connectedness.

Exploratory Aim: Explore differential response with respect to race/ethnicity (Black versus White adults); age (older versus younger adults); and psychiatric diagnosis (schizophrenia-spectrum vs. mood disorders).

Exploratory Hypothesis: Effect sizes for the I-IMR module versus generic support calls alone will be even greater among Blacks v. Whites, older (55+) v. younger adults, and people with schizophrenia-spectrum v. mood disorders.

3. Study Design

The proposed study is to compare I-IMR and CDSMP in improving outcomes of importance to the target population of people with SMI: optimizing personal physical and mental health, being an active agent in determining personal physical and mental health wellness goals, decreasing risk of early mortality, and minimizing use of the ER and hospitals. A secondary objective is to learn whether psychiatric diagnosis and/or age interacts with treatment, specifically, whether treatment effects vary more for participants with schizophrenia or older age. Consistent with a truly pragmatic trial, inclusion criteria are broad and exclusion criteria are limited. Participants will be randomized, stratified by diagnosis (schizophrenia spectrum vs. mood disorder) and age group (age 18-49 vs. age 50+).

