These interviews will inform development of the curriculum for the 3-session I-IMR module on COVID-19 and other viral diseases. This component of the project will also involve development of the primary outcome measure, given that no appropriate measure of COVID-19 knowledge and use of behaviors to avoid catching and spreading disease was available. After finalizing the curriculum for the 3-session I-IMR module, interventionists will be trained to deliver it by phone or video. We will record the sessions to permit supervision and fidelity assessment by the co-developers of I-IMR. All participants have already consented to audiotaping or videotaping of IIMR sessions. Research staff will conduct baseline, 6- and 12-week assessments by phone with all participants (75 I-IMR and 75 CDSMP participants). (Site Coordinators will first complete informed consent to participate in this project, by phone using the procedure described below). We will work with the statisticians from the I'M Well project to complete data analyses.

Site Coordinators will contact individuals who have been randomized to I-IMR and CDSMP to invite them to participate in this component of the project. I-IMR group participants will be offered the 3 session I-IMR module and asked to participate in a phone-based assessment no more than one week prior to receiving the intervention (baseline), a second assessment no more than two weeks after completing the 3 sessions (6 week assessment), and a third assessment approximately 12 weeks after receiving the last session of the module (12 week assessment). CDSMP group participants are receiving usual care, which includes generic supportive telephone calls from agency staff. They will be asked to participate in phone-based assessments on the same schedule as the I-IMR participants. For both groups (I-IMR & CDSMP), Site Coordinators will call participants to review a description of the project in the consent form. Consent to participate will be obtained by phone.

Interventions to be Compared

IIMR (Integrated Illness Management and Recovery vs. CDSMP (Stanford Chronic Disease Self-Management Program)

Overview of Integrated Illness Management and Recovery (I-IMR): I-IMR combines 4 evidence-based psychosocial interventions for SMI: (1) *psychoeducation*, which improves knowledge about

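### The COVID component's primary aim and exploratory hypothesis claim a module effect, but the design compares I-IMR plus module with CDSMP plus usual support calls, among people who consent after randomization

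*Combined protocol and SAP*

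**What the plan says.** Section 2 (COVID-19 Enhancement Primary Aim) states: "we will evaluate the impact of the module by comparing participants assigned to I-IMR (n=75) to participants assigned to CDSMP (n=75"). The exploratory hypothesis in the same section names the contrast as "Effect sizes for the I-IMR module versus generic support calls alone". The primary and secondary hypotheses between them are worded differently, as I-IMR participants against CDSMP participants.

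The background text just before section 2 says who gets the module: "75 participants (current and future participants assigned to I-IMR"). It also explains why the other arm does not: "We are not at liberty to add training on infectious viral diseases to CDSMP". The role of that arm is stated openly: "The CDSMP participants are essential to the study as they serve as the comparison group".

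Section 3 (Study Design, COVID component) describes enrolment: "Site Coordinators will contact individuals who have been randomized to I-IMR and CDSMP to invite them". It then says "I-IMR group participants will be offered the 3 session I-IMR module", with phone assessments around it. For the other arm, "CDSMP group participants are receiving usual care, which includes generic supportive telephone calls from agency staff", and those participants are asked only for assessments on the same schedule.

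Section 4 (COVID Component Analyses) fits a covariance pattern model with group, time and their interaction, and reads a significant interaction as I-IMR being superior to CDSMP. The only potential covariates named are depression, anxiety and fear of COVID.

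**The concern.** Two features separate the claimed effect from the one estimated.

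First, the module coincides completely with the parent arm. Everyone offered it was assigned to I-IMR, and no one assigned to CDSMP can receive it. A difference between groups therefore reflects the module together with whatever else differs between the two programs during follow-up. The word *alone* in the exploratory hypothesis does not fit either, because the comparators were assigned to CDSMP.

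Second, the analysis set is formed by consent given after randomization, to an offer that differs by arm: a program plus assessments, or assessments only. Randomization balances everyone assigned, not the subsets who accept different offers. Starting the clock at a component baseline removes differences in level at that point. It does not remove differences in subsequent change that arise from concurrent parent-program exposure or from who agreed to join.

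At stake is what can be concluded. A positive interaction could be reported as proof that the module works, when the design supports a statement about the combined package in a consenting subset.

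**Working it through.** **1. The plan's own figure.** Section 4 gives 80% power for an effect size of 0.46 with 75 per arm, 10% attrition and two-sided alpha 0.05. For a single-visit comparison the detectable effect is (1.960 + 0.842) × √(2/n).
- n = 75: 2.802 × 0.1633 = 0.4575, which rounds to 0.46.
- n = 75 × 0.9 = 67.5: 2.802 × 0.1721 = 0.482.

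So 0.46 is recovered here only without the stated attrition. That is a separate matter. The figure serves below only as a yardstick, and nothing in this point depends on it.

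**2. Claim against contrast.**

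| Statement | Contrast named |
|---|---|
| Primary aim (section 2) | effect of the module, by comparing arms |
| Primary and secondary hypotheses (section 2) | I-IMR vs CDSMP |
| Exploratory hypothesis (section 2) | module vs support calls alone |
| Inference (section 4) | I-IMR vs CDSMP |
| Groups formed (background, section 3) | I-IMR + module vs CDSMP + usual care with calls, consenters only |

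The first and third rows claim more than the last row delivers.

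**3. Where the parent program could intrude.** I-IMR has 16 sessions and CDSMP has 6, so exposure to the main-trial programs during component follow-up may differ. In the I-IMR curriculum (section 3, Interventions to be Compared, Table 1), Module 6 covers social support and Module 10 covers using the health care system and responding to emergencies. These lie close to the secondary outcomes of social connectedness and healthcare use. No module covers infectious disease, so confounding is less plausible for the primary outcome of COVID-specific knowledge and behavior.

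**4. Selective consent, under assumed values.** The component needs 75 of 300 per arm (25%). Consent rates are not given. Suppose consent is decided wholly by a standard normal motivation trait, with the top fraction p consenting. The mean trait among consenters is m(p) = φ(z)/p, where z is the cut-off.
- 60% (I-IMR): 0.3863/0.60 = 0.644.
- 40% (CDSMP): 0.3863/0.40 = 0.966.
- Gap: 0.966 − 0.644 = 0.322 SD, with the CDSMP consenters the more motivated.

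If the trait correlates r with improvement, the bias is r × gap: 0.3 × 0.322 = 0.10 and 0.5 × 0.322 = 0.16 SD, **against** I-IMR. If 0.46 is in the same SD units, that is 21% to 35% of it.

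Other assumptions give other answers:
- Rates reversed (40% I-IMR, 60% CDSMP): same size, in favor of I-IMR.
- 55% I-IMR, 45% CDSMP: gap about 0.16, bias about 0.05 to 0.08 SD.
- 60/40, but consent propensity correlating only 0.5 with the trait: gap halves to 0.16.
- Equally selective consent in both arms: zero.

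**5. What a non-module difference does to the test.** With 67.5 per arm, a single-visit contrast (standard error √(2/67.5) = 0.172) and no module effect, an arm difference from other causes of 0.10 SD gives significance in 8.9% of trials instead of 5%. At 0.15 SD it is 14.0%. These hold for a difference in either direction and are illustrations only.

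**The case against.** The best defense has four parts.
- The plan discloses the constraint. The team may not add content to CDSMP, and CDSMP is kept as comparator to preserve the comparative effectiveness design that the funder requires.
- The primary and secondary hypotheses and the section 4 inference are arm contrasts, and the primary aim itself says which assigned groups are compared.
- The primary outcome is COVID-specific, the parent I-IMR curriculum does not cover it, and the interaction with time discounts whatever was gained before the component baseline.
- Differential uptake is speculative. Section 12 lists the same payments without distinction by arm, and the CDSMP group's lighter task could raise its uptake.

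All of this stands, and it narrows the point. It does not make the module a randomized factor, and it does not restore the protection of randomization among consenters.

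Three stronger readings are tempting. A reader might infer that selection inflates the I-IMR result. The documents give no direction, and in the 60/40 example the bias runs the other way. A reader might infer that the component can support no conclusion. It can support one about the arms as delivered, among consenters, subject to the selection caveat. A reader might also take it as stated that people consent knowing their arm. No sentence says so. It is a reasonable inference from invitation after assignment to openly different programs, with the project described at consent.

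**Conclusion.** The concern holds for the primary aim and the exploratory hypothesis. Both claim an effect of the module, while the design delivers assignment to I-IMR plus module against CDSMP plus usual support calls, among people who agreed after randomization to unequal offers. It does not extend to the primary and secondary hypotheses or to the section 4 inference, which already name the arms, although those too are estimated only in consenters.

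Parent-program confounding is most plausible for social connectedness and healthcare use, and less so for the primary outcome. The documents do not determine the size or sign of selection bias. The range of 0.10 to 0.16 SD against I-IMR rests on assumed 60/40 consent, selection wholly on one trait, and a correlation of 0.3 to 0.5 with improvement. Weaker selection or closer rates shrink it. The change is worth making because it is cheap and brings the claim into line with the design.

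**What to change.** 1. Reword the primary aim, the exploratory hypothesis and the planned conclusion as *assignment to I-IMR plus module versus CDSMP plus usual support calls, among consenting participants*.
2. Add the randomization strata (diagnosis, age group) and parent-trial baseline PAM, PAM-MH and IMRS to the covariance pattern model, each with its interaction with time. Main effects alone would shift levels and leave the group-by-time term largely unadjusted.
3. Report numbers invited and consented by arm, with baseline characteristics of each set.
4. Report main-trial session completion at component baseline descriptively or in a sensitivity analysis. It arises after randomization and is tied to arm (16 against 6 sessions), so it should not be a main covariate. A random order of invitation is not needed, because it would not address selective consent.

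Cost: wording, invitation and consent counts, and covariates the main trial already collects. With time as three categories, five covariates add 5 main effects and 5 × 2 = 10 interaction terms, 15 parameters in all. The claim becomes narrower, and adjustment handles only measured differences.
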